3 PATIENT ELIGIBILITY

The target population for this study is patients with high risk or BCG-refractory non-muscle invasive bladder cancer. This will be a single-center trial conducted in the Northwestern

NU Study Number: NU 15U06
Merck Study Number: 3475-265

Medicine Developmental Therapeutics Institute in conjunction with the Department of Urology of Northwestern University at Northwestern Medicine.

Up to 24 evaluable subjects will be needed for this trial, therefore up to a total of 27 may be enrolled in order to achieve the necessary number of evaluable subjects. BCG-refractory is defined as tumor recurrence within 6 months of receiving at least 2 courses of intravesical BCG (at least 5 or 6 inductions and at least 2 or 3 maintenance doses) or T1 high grade disease at the first evaluation following induction BCG alone (at least 5 or 6 induction doses). Therefore, patients who develop a recurrence of bladder cancer during maintenance treatment period with BCG will be also eligible to the present study. However, patients who were not able to complete prior induction BCG treatment because of intolerable toxicities and developed a recurrence will not be eligible for this trial given increased risk of adverse events with repeated exposure.

On average, 1-2 high risk or BCG-refractory potentially eligible patients are seen per month in the Urology clinic, and it is anticipated that one patient will be accrued every 2-3 months. Potential patients may be referred to the Principal Investigator (PI) at Northwestern University, [name], at [contact]. In addition, the sub-investigators have significant experience and collaborations with nearby university and community urology groups to help provide additional referrals for this high priority study when activated.

Eligibility will be evaluated by the study team according to the following criteria. Eligibility waivers are not permitted. Subjects must meet all of the inclusion and none of the exclusion criteria to be registered to the study. Study treatment may not begin until a subject is registered. Please refer to Section 10.3 for complete instructions regarding registration procedures.

3.1 Inclusion Criteria

3.1.1 Patients must have a histologically documented recurrence of non-muscle-invasive bladder carcinoma (T1HG, T1HG after reTUR or BCG refractory; if patient has received BCG they can be Ta, Tis, or T1)

Note: Gross disease is not allowed, however positive urine cytology and carcinoma in situ is permitted.

3.1.2 Patients must be BCG-unresponsive. A patient is BCG-unresponsive if they meet one or more of the following criteria:

- Patient has persistent or recurrent high-grade Ta/CIS/ urothelial carcinoma after completing therapy with at least induction BCG (≥ 5 doses) and first round maintenance or second induction BCG (≥ 2 doses). Patient has high grade T1 urothelial carcinoma after induction BCG (≥ 5 doses) only or after induction BCG (≥ 5 doses) and first round maintenance or second induction BCG (≥ 2 doses).
- Patient is disease-free at completion of BCG (i.e., complete response) but then experiences a high-grade recurrence before or at the 6 month follow-up cystoscopy.
- Recurrence after treatment with at least 3 doses of a BCG refractory agent (for example, though not limited to, gemcitabine, docetaxel, valrubicin or an interferon adenovirus).

3.1.3 Patients must have received one course of induction treatment with BCG (4-6 weekly doses), irrespective of the interval since last treatment. Patients are allowed to have received any number of prior chemotherapy instillations.

NOTE: Patients may have received prior intravesical interferon.

NU Study Number: NU 15U06
Merck Study Number: 3475-265

3.1.4 Patients must be age \geq 18 years.

3.1.5 All patients positive for invasion must have imaging (CT scan or MRI) documenting normal upper urinary tracts and absence of locally advanced bladder cancer within 60 days prior to study registration.

3.1.6 Have a performance status of 0-1 on the ECOG Performance Scale

3.1.7 Patients must have adequate organ and bone marrow function within 14 days prior to registration, as defined below:

System	Laboratory Value
Hematological	
Absolute neutrophil count (ANC)	\geq 1,500 /mcL
Platelets	\geq 100,000 / mcL
Hemoglobin	\geq 7 g/dL or \geq 5.6 mmol/L
Renal	
Serum creatinine OR Measured or calculated ^a creatinine clearance (GFR can also be used in place of creatinine or CrCl)	\leq 1.5 X upper limit of normal (ULN) OR \geq 60 mL/min for subject with creatinine levels $>$ 1.5 X institutional ULN
Hepatic	
Serum total bilirubin	\leq 1.5 X ULN OR Direct bilirubin \leq ULN for subjects with total bilirubin levels $>$ 1.5 ULN
AST (SGOT) and ALT (SGPT)	\leq 2.5 X ULN
Coagulation	
International Normalized Ratio (INR) or Prothrombin Time (PT)	\leq 1.5 X ULN unless subject is receiving anticoagulant therapy as long as PT or PTT is within therapeutic range of intended use of anticoagulants
Activated Partial Thromboplastin Time (aPTT)	\leq 1.5 X ULN unless subject is receiving anticoagulant therapy as long as PT or PTT is within therapeutic range of intended use of anticoagulants

^aCreatinine clearance should be calculated per institutional standard.

3.1.8 Females of child-bearing potential (FOCBP) and males must agree to use adequate contraception (e.g. hormonal or barrier method of birth control; abstinence) prior to study entry, for the duration of study participation, and for 120 days following completion of therapy. Should a female patient become pregnant or suspect she is pregnant while participating in this study, she should inform her treating physician immediately.

NOTE: A FOCBP is any woman (regardless of sexual orientation, having undergone a tubal ligation, or remaining celibate by choice) who meets the following criteria:

- *Has not undergone a hysterectomy or bilateral oophorectomy*
- *Has had menses at any time in the preceding 12 consecutive months (and therefore has not been naturally postmenopausal for > 12 months)*

3.1.9 FOCBP must have a negative urine or serum pregnancy test within 7 days prior to receiving the first dose of study medication. If the urine test is positive or cannot be confirmed as negative, a serum pregnancy test will be required.

3.1.10 Patients must have the ability to understand and the willingness to sign a written informed consent prior to registration on study.

3.1.11 Patients must be willing and able to comply with scheduled visits, treatment and assessments.

3.2 Exclusion Criteria

3.2.1 Patients who have had chemotherapy, targeted small molecule therapy, or radiation therapy within 2 weeks prior to study Day -14 or who have not recovered (to ≤ Grade 1 or baseline) from adverse events due to a previously administered agent are not eligible.

Note: Subjects with ≤ Grade 2 neuropathy are an exception to this criterion and do qualify for the study.

Note: If subject received major surgery within 4 weeks prior to Day -14, they must have recovered adequately from the toxicity and/or complications per PI discretion.

3.2.2 Patients who have received any other investigational agent ≤ 28 days prior to registration are not eligible.

3.2.3 Patients who have received a prior monoclonal antibody ≤ 28 days prior to study Day -14 are not eligible.

3.2.4 Patients who have not recovered (to ≤ Grade 1 or baseline) from adverse events due to agents administered ≥ 28 days earlier are not eligible.

3.2.5 Patients who have a diagnosis of immunodeficiency (per PI discretion) or who have received treatment with systemic immunosuppressive medications (including but not limited to prednisone, cyclophosphamide, azathioprine, methotrexate, thalidomide, and anti-tumor necrosis factor [anti-TNF] agents) ≤ 14 days prior to study registration are not eligible.

NOTE: Patients who have received acute, low-dose, systemic immunosuppressant medications (e.g., one-time dose of dexamethasone for nausea) may be enrolled in the study. The use of inhaled corticosteroids and mineralocorticoids (e.g., fludrocortisone) is allowed.

3.2.6 Patients who have a history of allergic reactions attributed to compounds of similar chemical or biologic composition to pembrolizumab are not eligible.
AND/OR

Patients who have had prior exposure to compounds of similar chemical or biologic composition to pembrolizumab are not eligible.

3.2.7 Patients who have documentation of an uncontrolled intercurrent illness (as noted in their medical records) including, but not limited to any of the following, are not eligible:

- Ongoing or active infection requiring systemic treatment
- Symptomatic congestive heart failure (New York Heart Association cardiac disease Class III or IV)
- Unstable angina pectoris
- Myocardial infarction within the previous 3 months
- Unstable cardiac arrhythmias

NU Study Number: NU 15U06
Merck Study Number: 3475-265

- Psychiatric illness/social situations that would limit compliance with study requirements
- Any other illness or condition that the treating investigator feels would interfere with study compliance or would compromise the patient's safety or study endpoints

- 3.2.8 Female patients who are pregnant or nursing are not eligible.
- 3.2.9 Patients who have a history of allergic reactions attributed to compounds of similar chemical or biologic composition to BCG are not eligible.
- 3.2.10 Patients who have had an active infection requiring systemic therapy \leq 7 days prior to Day -14 are not eligible UNLESS they are symptom-free and have a negative culture at the time of dosing on Day -14.
- 3.2.11 Patients who received a live, attenuated vaccine \leq 28 days before study registration or are anticipated to require such a live attenuated vaccine are not eligible.

NOTE: Influenza vaccination should be given during influenza season only (approximately October to March). Patients must not receive live, attenuated influenza vaccine (e.g., FluMist) \leq 28 days prior to study registration or at any time during the study.

- 3.2.12 Patients who are known to be (i.e. documented in medical records) human immunodeficiency virus (HIV) positive are not eligible.
- 3.2.13 Patients with active tuberculosis are not eligible.
- 3.2.14 Patients with known active hepatitis B (chronic or acute; defined as having a positive hepatitis B surface antigen [HBsAg] test at screening) or hepatitis C are not eligible.

NOTE: Patients with past hepatitis B virus (HBV) infection or resolved HBV infection (defined as the presence of hepatitis B core antibody [HBc Ab] and absence of HBsAg) are eligible. HBV DNA must be obtained in these patients 14 days prior to study registration.

NOTE: Patients positive for hepatitis C virus (HCV) antibody are eligible only if polymerase chain reaction is negative for HCV RNA.

- 3.2.15 Patients who have a history of severe allergic, anaphylactic, or other hypersensitivity reactions to chimeric or humanized antibodies or fusion proteins are not eligible.
- 3.2.16 Patients with an active autoimmune disease requiring ongoing systemic treatment (i.e. with use of disease modifying agents, corticosteroids or immunosuppressive drugs) are not eligible.

NOTE: A minimum 14 day washout period is required for eligibility.

NOTE: Replacement therapy (e.g. thyroxine, insulin, or physiologic corticosteroid replacement therapy for adrenal or pituitary insufficiency, etc.) is not considered a form of systemic treatment.

NU Study Number: NU 15U06
Merck Study Number: 3475-265

3.2.17 Patients with history of interstitial lung disease or active, non-infectious pneumonitis are not eligible.

NOTE: History of radiation pneumonitis in the radiation field (fibrosis) is permitted.

3.2.18 Patients who receive treatment with systemic immunostimulatory agents (including but not limited to IFNs, IL-2) within 6 weeks or five half-lives of the drug, whichever is shorter, prior to study registration are not eligible.

3.2.19 Patients who received prior treatment with an anti-PD-1, anti-PD-L1, anti-PD-L2, anti-CD137, or anti-Cytotoxic T-lymphocyte-associated antigen-4 (CTLA-4) antibody (including ipilimumab or any other antibody or drug specifically targeting T-cell co-stimulation or checkpoint pathways) are not eligible.

3.2.20 Patients who have a history of another malignancy within the previous 12 months are not eligible.

Note: Exclusions include:

- *Patients with a disease-free interval of > 12 months and/or have not received systemic therapy for > 12 months for another malignancy are eligible.*
- *Basal cell carcinoma of the skin, squamous cell carcinoma of the skin, or in situ cervical cancer that has undergone potentially curative therapy are eligible.*
- *If another malignancy is incidentally found during study eligibility work up and does not require treatment the patient will be eligible. This should be clearly documented in the medical record at the time of study registration.*

3.2.21 Patients who have a history of an allogeneic tissue/solid organ transplant are not eligible.

4 TREATMENT PLAN

4.1 Overview

Treatment will be administered on an outpatient basis. Treatment will be divided into pre-induction, induction and maintenance therapy phases. Two weeks prior to induction, subjects will receive the first intravesical instillation of pembrolizumab (week -2). During induction therapy, patients will receive standard intravesical instillation with BCG once weekly for 6 weeks (total of 6 BCG instillations). Patients will also be treated with concomitant pembrolizumab, given intravesically every 2 weeks during the induction period (total of 3 pembrolizumab instillations; weeks 0, 2, and 4). The maintenance phase starts at week 7 and continues up to 1 year (last dose and cystoscopy at week 49). Intravesical BCG and intravesical pembrolizumab will be given every 2 weeks for the first 12 weeks of maintenance therapy (weeks 7, 9, 11, 13, 15, 17 for a total of 6 doses) and then every 4 weeks thereafter (weeks 21, 25, 29, 33, 37, 41, 45 and 49 for a total of 8 doses) until completion of treatment or early discontinuation for any reason.

Cystoscopies will be performed 8 weeks (approximately 2 months) from the end of the induction period (week 17) and will be repeated at 8-week intervals until week

NU Study Number: NU 15U06
Merck Study Number: 3475-265

49. If ambulatory cystoscopy reveals any abnormal finding requiring further investigation, BCG and/or pembrolizumab administration will be suspended until clinical investigation is completed. Tumor progression will be defined as positive transurethral resection and/or biopsy including tumor stage progression, muscle infiltration or metastasis. Should a bladder cancer progression be confirmed, the subject will be off treatment and off-study. Otherwise, subject will be able to resume study treatments approximately 4 weeks (per PI discretion) after any bladder biopsy to allow appropriate healing. NOTE: the PI will review and confirm when appropriate healing has occurred to allow resumption of treatment. Any patient who has a high-risk lesion resected on a follow-up cystoscopy must be removed from study treatment.

This phase I study will utilize a 3+3 dose escalation scheme for the study drug pembrolizumab with an initial dose of 1 mg/kg given intravesically to the first cohort of three subjects. Details regarding dose escalation can be found in section 4.3. This study will enroll a maximum of 18 evaluable subjects. Evaluable subjects for toxicity will be those who receive at least one dose of the study drug. Evaluable subjects for response are those who meet the minimum treatment and safety evaluation requirements of the study: i. the subject has received the six doses of BCG and three doses of pembrolizumab planned for the induction phase and has sufficient safety data available to assess the occurrence of dose limiting toxicities; ii. the subject has received at least 1 dose of pembrolizumab out of the total 11 doses planned during the maintenance period.

There is a possibility of adding an expansion cohort of up to 10 subjects to further define safety and efficacy of pembrolizumab. This will be determined by Merck after completion of the dose escalation phase.

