8.4	Peripheral blood cytokine assays and lymphocyte phenotypes	51
8.5	NGS.....	50
8.6	Specimen Banking.....	51
9	STATISTICAL CONSIDERATIONS	51
10	STUDY MANAGEMENT.....	52
10.1	Institutional Review Board (IRB) Approval and Consent.....	52
10.2	Amendments	52
10.3	Registration Procedures	53

[figure not shown]
NU Study Number: NU 15U06
Merck Study Number: 3475-265

10.4	Data Management and Monitoring/Auditing	53
10.5	Adherence to the Protocol	53
10.6	Investigator Obligations	54
10.7	Publication Policy	54
11	APPENDICES.....	55
11.1	Appendix A	55
11.2	Appendix B	56
11.3	Appendix C	57
12	References.....	72

LIST OF ABBREVIATIONS

AE	Adverse Event
ALT	Alanine Aminotransferase
ALC	Absolute Lymphocyte Count
AST	Aspartate Aminotransferase
BUN	Blood Urea Nitrogen
BCG	Bacillus Calmette-Guerin live attenuated Mycobacterium bovis
CBC	Complete Blood Count
CMP	Comprehensive Metabolic Panel
CR	Complete Response
CT	Computed Tomography
CTCAE	Common Terminology Criteria for Adverse Events
DLT	Dose Limiting Toxicity
DSMB	Data and Safety Monitoring Board
ECOG	Eastern Cooperative Oncology Group
H&PE	History & Physical Exam
IV (or iv)	Intravenously
MTD	Maximum Tolerated Dose
NMIBC	Non-Muscle-Invasive Bladder Cancer
ORR	Overall Response Rate or Objective Response Rate
OS	Overall Survival
PK	Pharmacokinetic
PD	Progressive Disease
PFS	Progression Free Survival
PO (or p.o.)	Per os/by mouth/orally
PR	Partial Response
reTUR	Repeat transurethral resection
SAE	Serious Adverse Event
SD	Stable Disease
SGOT	Serum Glutamic Oxaloacetic Transaminase
SPGT	Serum Glutamic Pyruvic Transaminase
WBC	White Blood Cells

STUDY SCHEMA

¹ Clinical follow-up for disease recurrence and survival will occur according to this schedule: every 3 months x 2 years, then every 4 months x 2 years, then every 6 months x 2 years, then yearly. Patients will remain on study follow-up until end of trial, withdrawal, or death (whichever occurs first).

Phase		Pre-induction	Induction Phase						Maintenance Phase															
Week		-2	0	1	2	3	4	5	7	9	11	13	15	17	21	25	29	33	37	41	45	49		
Treatment		MK	BCG +MK	BCG	BCG +MK	BCG	BCG +MK	BCG	BCG +MK	BCG +MK	BCG +MK	BCG +MK	BCG +MK	BCG +MK +Cysto	BCG +MK	BCG +MK +Cysto	BCG +MK	BCG +MK +Cysto	BCG +MK	BCG +MK	BCG +MK +Cysto	BCG +MK	BCG +MK +Cysto	
PKs (blood & urine*)		X					X																	
Creatinine	Urine	X	X	X	X	X	X	X	X	X	X	X	X	X	X	X	X	X	X	X	X	X	X	
Cytokines & Flow Studies [#]	Urine	X	X	X	X	X	X	X	X	X	X	X	X	X	X	X	X	X	X	X	X	X	X	
	Blood	X	X												X									

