Patients presenting with recurrences after BCG have limited therapeutic options. Radical cystectomy or bladder-preserving strategies are generally recommended especially for high-grade recurrent tumors. These surgical options have significant long-term morbidity, impact on quality of life and the majority of these patients have multiple comorbid conditions (i.e., cardiovascular disease, renal insufficiency) making them high-risk surgical candidates. It is acceptable to repeat BCG treatment for low-grade and selected high-grade tumors especially if the recurrence develops more than 1 year after treatment. Limited experience with BCG plus interferon- α suggests that it can be used for recurrent tumors after 1 or more BCG courses resulting in disease free rate of approximately 54-66% at 24 months ^{8,9}. A phase III trial compared gemcitabine and mitomycin C for patients with unsuccessful BCG treatment ¹⁰. Intravesical gemcitabine was better tolerated but 28% of patients still developed a recurrence during the 36 months follow up compared to 39% among those receiving mitomycin C ¹⁰. These results suggest alternative treatments for BCG –refractory patients have limited long-term efficacy. Therefore, a radical cystectomy and its associated 28% morbidity and 2.5% mortality risks continues to offer the highest cure rate in this setting ¹¹.

While the mechanism of action of BCG is not understood, recognition of the tumor by an intact immune system is critical to the anti-tumor response elicited by BCG. In fact, patient inability to mount an immunogenic tumoricidal response when treated with BCG has been proposed as one of the mechanisms of recurrences or residual disease. This hypothesis might reflect the immune suppression induced by tumor

NU Study Number: NU 15U06
Merck Study Number: 3475-265

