4.9.2 Follow-Up Visits

After discontinuing trial therapy, patients will be followed clinically for disease recurrence and survival according to the below schedule. There is no specific limit on the length of follow-up, as it is intended to follow all patients for survival.

After the last dose of trial therapy, follow patients:

- Every 3 months (\pm 30 days) during years 1 and 2;
- Every 4 months (\pm 60 days) during years 3 and 4;
- Every 6 months (\pm 60 days) during years 5 and 6;
- Every 12 months (\pm 90 days) thereafter;
- Or until death, withdrawal, or end of study (whichever occurs first).

Information regarding post-study anti-neoplastic treatment will be collected if new treatment is initiated.

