4.10 Removal of Patients from Protocol Therapy and/or Study as a Whole

Patients can be taken off the study treatment and/or study at any time at their own request, or they may be withdrawn at the discretion of the investigator for safety, behavioral or administrative reasons. The reason(s) for discontinuation will be documented and may include:

- Patient voluntarily withdraws from treatment (follow-up permitted);
- Patient withdraws consent (termination of treatment with no follow-up);
- Patient is unable to comply with protocol requirements (follow-up permitted);
- Patient demonstrates disease progression (follow-up permitted);
- Patient undergoes resection of a high risk lesion on a study cystoscopy

NU Study Number: NU 15U06
Merck Study Number: 3475-265

- Patient experiences toxicity that makes continuation in the protocol unsafe (follow-up permitted);
- Treating physician concludes that continuation on the study would not be in the patient's best interest (follow-up permitted);
- Patient becomes pregnant;
- Development of second malignancy that requires treatment, which would interfere with this study (follow-up permitted);
- Lost to follow-up.

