20. Whether a patient completes the full year of therapy or discontinues early for any reason, an end-of-treatment visit should be conducted approximately 30 days (\pm 7 days) from the last dose of study drug.
21. Once off treatment, patients will be followed clinically for disease recurrence and survival according to the following schedule. After the last dose of trial therapy, follow patients every 3 months (\pm 30 days) during years 1 and 2, every 4 months (\pm 60 days) during years 3 and 4, every 6 months (\pm 60 days) during years 5 and 6, and every 12 months (\pm 90 days) thereafter, or until death, withdrawal, or end of study (whichever occurs first). If a patient discontinues treatment (for any reason other than disease recurrence) prior to completing the full year of therapy, they will immediately enter into the clinical follow-up phase.

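### Section 4.1 takes progressed subjects off-study although the plan elsewhere follows them for survival, so OS can be cut at progression; Section 9 also gives two PFS censoring dates

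*Combined protocol and SAP*

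**What the plan says.** **Survival follow-up after progression**

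- Section 4.1 (Overview): "Should a bladder cancer progression be confirmed, the subject will be off treatment and off-study".
- Study Schema, footnote 1: "Patients will remain on study follow-up until end of trial, withdrawal, or death (whichever occurs first").
- Section 4.9.2: "There is no specific limit on the length of follow-up, as it is intended to follow all patients for survival".
- Section 4.10, in the list of reasons for discontinuation: "Patient demonstrates disease progression (follow-up permitted").
- Section 5, footnote 21, opening: "Once off treatment, patients will be followed clinically for disease recurrence and survival according to the following schedule". Its last sentence concerns patients who discontinue treatment ("for any reason other than disease recurrence) prior to completing the full year of therapy, they will immediately enter into the clinical follow-up phase".

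Section 2.3.9 makes OS an exploratory endpoint covering death from any cause. Section 9 ends OS time at the earliest of death, completed study participation or loss to follow-up. A subject not observed to die is censored when survival status was last documented.

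**PFS and new anti-cancer therapy**

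Section 9 first censors a subject who starts new therapy without earlier progression on the day that therapy starts. A second sentence, which also names the start of new therapy, censors at the last disease assessment.

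**The concern.** Section 4.1 cannot easily be read as ending treatment only. Its sentence already says that treatment stops, so going off-study must add something. The same section uses narrower words, removal from study treatment, for a patient who has a high-risk lesion resected. The title of Section 4.10 likewise separates protocol therapy from the study as a whole.

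If a site applies Section 4.1, survival data stop at progression. If the analyst then treats going off-study as completed participation, OS is censored there. Subjects who progress are likely to have higher mortality than those who do not, so this censoring would be informative and the Kaplan-Meier curve biased upward. Many subjects could be involved, because Section 2.3.4 counts any positive resection or biopsy as progression.

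For PFS, the analyst has to choose between two stated dates, possibly after seeing the data.

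**Working it through.** **1. The plan's own figure.** The only operating characteristic given is the chance of escalating in the 3+3 design, (1−p)³ + 3p(1−p)²(1−p)³. It gives 90.6%, 49.4% and 17.2% at p = 10%, 30% and 50%, against the stated 91%, 49% and 17%. It reproduces, and this point does not touch it. OS and PFS have no stated power or target number of events, so the rest is an illustration.

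**2. Recurrence rates from Section 1.1.** For gemcitabine against mitomycin C after BCG failure, "28% of patients still developed a recurrence during the 36 months follow up compared to 39% among those receiving mitomycin C". For BCG plus interferon, "resulting in disease free rate of approximately 54-66% at 24 months". At constant hazard the annual rates are:

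- 1 − 0.72^(1/3) = 10.4%
- 1 − 0.61^(1/3) = 15.2%
- 1 − 0.66^(1/2) = 18.8%
- 1 − 0.54^(1/2) = 26.5%

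The range used is 10.4% to 26.5% per year. It is a guide only, because populations and treatments differ.

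**3. Model.** Illness-death with constant hazards, h(p) = −ln(1−p). Progression hazard: lp = h(0.104) or h(0.265). Death hazard before progression: d0 = h(0.03). Death hazard after progression: d1 = h(0.03), h(0.05), h(0.10) or h(0.20). All mortality rates are assumptions; the documents give none for this setting. With a = lp + d0:

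- True OS(t) = exp(−a·t) + [lp/(a−d1)]·[exp(−d1·t) − exp(−a·t)]
- Kaplan-Meier with every progressed subject censored at progression = exp(−d0·t) = 0.97³ = 0.913 at 3 years

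| Annual mortality after progression | True 3-year OS (recurrence 10.4% / 26.5%) | Overstatement, all lost (points) | Overstatement, half lost (points) |
|---|---|---|---|
| 3% | 0.913 / 0.913 | 0 / 0 | 0 / 0 |
| 5% | 0.904 / 0.893 | 0.8 / 1.9 | 0.4 / 0.7 |
| 10% | 0.885 / 0.847 | 2.8 / 6.6 | 1.3 / 2.4 |
| 20% | 0.848 / 0.762 | 6.5 / 15.1 | 2.9 / 5.4 |

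The half-lost column integrates the hazard (N·d0 + 0.5·P·d1)/(N + 0.5·P), where N is the fraction progression-free and P the fraction alive after progression, with loss unrelated to prognosis.

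Among 24 subjects, 6.4 to 13.9 would progress by 3 years. If all are lost, the uncounted deaths are 0.5–1.2, 1.0–2.3 and 1.9–4.3 at 5%, 10% and 20%. With an assumed faster progression of 30–50% per year and all lost, the overstatement is 2–3, 7–11 and 17–25 points.

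**4. PFS dates.** The two dates can differ by up to:

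- 25 − 17 = 8 weeks between scheduled cystoscopies on treatment;
- 17 − (−2) = 19 weeks before the first one, if none is done earlier;
- a nominal 3 months in follow-up years 1–2 and 4 months in years 3–4.

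One affected subject changes the Kaplan-Meier drop at an event inside that gap by about 1/23 − 1/24 = 0.2 points with 24 at risk, and by at most 1/9 − 1/10 = 1.1 points with 10 at risk.

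**The case against.** The intent is not in doubt. The change log for Amendment 10, which added OS, says that the schema, Section 4.9.2 and the procedures table were changed to allow survival follow-up after progression. Section 4.1 looks like a sentence left behind. OS is cut only if sites follow it against the other passages and the analyst equates going off-study with completed participation. Section 9 also already censors at the last documented survival status, which is close to the proposed fix.

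The large gaps need 20% annual mortality and every progressed subject lost, and no document supplies those figures. Section 1.1 reports 38% recurrence and 3% bladder-cancer death after BCG, about 3/38 = 8 such deaths per 100 recurrences, though in a different population and over an unstated period. Section 9 plans medians, not 3-year rates, and with 24 subjects the standard error of 3-year OS is about 6 to 9 points. On PFS, the first sentence could be read as the specific rule and the second as a general fallback.

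Much of this stands: lost deaths are a risk and not a certainty, the larger gaps are assumption-driven, and the PFS effect is small. Three parts do not:

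- Censoring at last documented status cannot recover deaths that were never collected because follow-up had ended.
- Sampling error does not excuse bias, which the planned confidence intervals do not reflect.
- The second PFS sentence names new therapy itself, so it is not merely a fallback.

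**Conclusion.** The concern holds. Section 4.1 conflicts with the follow-up passages, and Section 9 leaves open when participation ends, so following the text as written can cut OS at progression. The bias is zero if the follow-up passages are applied or if progression does not raise mortality. Otherwise it depends on the assumed mortality after progression and on how many progressed subjects are lost. At 10% annual mortality after progression it is 1.3 to 2.4 points of 3-year OS with half lost and 2.8 to 6.6 with all lost, using the recurrence rates of Section 1.1.

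Footnote 21 is secondary: its last sentence excepts recurrence only from immediate entry into follow-up and is at most ambiguous. The two PFS dates cannot both be followed, but they conflict only for subjects who start new therapy without progression, who may be few.

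This should be corrected, at modest weight: OS and PFS are exploratory and descriptive, and the MTD, DLT and safety results do not depend on them.

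**What to change.** 1. Reconcile Section 4.1 with the schema, Section 4.9.2 and Section 4.10, so that a subject with confirmed progression stays in survival follow-up. The treatment-stopping rule stays as it is. Clarify the last sentence of footnote 21 to match.
2. In Section 9, define OS along these lines: *OS is the time from first trial therapy to death from any cause; subjects not known to have died are censored at the date last known alive; progression does not complete study participation.*
3. In Section 9, keep one PFS rule for new therapy before progression. For example: *PFS is censored at the last disease assessment on or before the start of new anti-cancer therapy or, if there is none after baseline, at the date of first dose.* The other stated date is also workable; what matters is that only one remains.

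The cost is wording in Section 4.1, footnote 21 and Section 9. No subjects or visits are added, since Section 4.9.2 already plans the follow-up. OS and PFS may look slightly less favourable. Under the example PFS rule, a subject who starts new therapy before any post-baseline assessment contributes no PFS time.
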